 - 1.3 statistical criteria of intergroup comparisons will be two-sided, equivalence criterion one-sided;
 - 1.4 calculation of sample size will be based on the assumptions on the expected effect declared in the primary efficacy criterion of the protocol;
 - 1.5 ratio between sample sizes of Tenoten and Placebo groups receiving similar dosing schemes will be 2:1 (1 Placebo patient 2 Tenoten patients);
 - 1.6 statistical analysis will utilize pooled Placebo group including Placebo with dosing scheme 2 tablets 2 times and Placebo group with dosing scheme 4 tablets 2 times a day, as the differences between Placebo groups with different dosing schemes are not suggested;
 - 1.7 the study is supposed to use three groups of statistical hypotheses; for this purpose probability of type I error α will be corrected by introducing the relevant correction for three hypotheses (α =0.05/3);
 - 1.8 statistical hypotheses will be as follows:
 - 1.8.1. null and alternative hypotheses on superiority of the study product with dosing scheme 2 tablets 2 times a day:

H₀: $\Delta \mu_{T1} = \Delta \mu_{\Pi}$

$H_a: \Delta \mu_{T1} \neq \Delta \mu_{\Pi},$

where $\Delta \mu_{\tau 1}$ – mean reduction (initial – final score) of HAM-A total score in Tenoten group with dosing scheme 2 tablets 2 times a day, $\Delta \mu_{\Pi}$ – mean reduction (initial – final score) of HAM-A total score in Placebo group;

1.8.2. null and alternative hypotheses on superiority of the study product with dosing scheme 4 tablets 2 times a day:

H₀: $\Delta \mu_{T2} = \Delta \mu_{\Pi}$

¹⁰ Holder of license: OOO "NPF "Materia Medica Holding", No. 70100045.

H_a: $\Delta \mu_{T2} \neq \Delta \mu_{\Pi}$,

where $\Delta \mu_{r2}$ – mean reduction (initial – final score) of HAM-A total score in Tenoten group with dosing scheme 4 tablets 2 times a day, $\Delta \mu_{\pi}$ – mean reduction (initial – final score) of HAM-A total score in Placebo group;

1.8.3. null and alternative hypotheses on equivalence of the study product with dosing scheme 2 tablets 2 times a day with the study product with dosing scheme 4 tablets 2 times a day:

$$\begin{split} H_0: & |\Delta \mu_{T1} - \Delta \mu_{T2}| \geq \delta \\ H_a: & |\Delta \mu_{T1} - \Delta \mu_{T2}| < \delta, \end{split}$$

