where μ_{T1} – mean reduction (initial – final score) of HAM-A total score in Tenoten group with dosing scheme 2 tablets 2 times a day, μ_{T2} – mean reduction (initial – final score) of HAM-A total score in Tenoten group with dosing scheme 4 tablets 2 times a day, δ – equivalence margin accepted as 0.15*M where M – mean total population score at baseline;

- 1.9 calculation of sample size for statistical criteria will be made using the group of formulas:
 - 1.9.1. calculation of sample size to evaluate superiority of the study product over placebo:

$$n_1=n_2=\frac{2(z_{\alpha/2}+z_\beta)^2\sigma^2}{\epsilon^2}$$

where $\mathbf{n_1}$, $\mathbf{n_2}$ is sample size for the study product group; ε – expected difference in mean reduction of the total score between Placebo and Tenoten groups; $\boldsymbol{\sigma}$ – standard deviation of mean reduction of the total score (calculated as standard deviation of difference between two uncorrelated random variables); $z_{\alpha/2}$ – tabular value of two-sided z-test for α value; z_{β} – tabular value of one-sided ztest for β value;

1.9.2. calculation of sample size for equivalence evaluation:

$$n_1 = n_2 = \frac{2(z_{\alpha} + z_{\beta/2})^2 \sigma^2}{(\delta - |\epsilon|)^2},$$

where $\mathbf{n_1}$, $\mathbf{n_2}$ is sample size for the study product group; ε – expected difference in mean reduction of the total score between Tenoten with dosing scheme 2 tablets 2 times a day and Tenoten with dosing scheme 4 tablets 2 times a day; $\boldsymbol{\sigma}$ – standard deviation of mean reduction of the total score (calculated as standard deviation of the difference between two uncorrelated random variables); z_{α} – tabular value of z-test for α value; z_{β} – tabular value of z-test for β value, δ – equivalence margin accepted as 0.15*M where M – mean total population score at baseline;

1.10 sample size will be determined using the formula:

N_{PP}=max{ n_i, all pairs of interest (i)},

where N_{PP} – Per Protocol sample size; n_i – result of calculation in cl. 1.6, i.e. the result for each of the three study hypotheses;

1.11 final sample size will be determined using the formula:

$$N_T = N_{PP} / (1 - C_w),$$

where N_T – final sample size; N_{PP} – result of calculation in cl. 1.7, i.e. the scheduled number of the subjects completing the study per protocol; C_w – withdrawal coefficient.

2. Assumptions on expected clinical study effects:

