Mean HAM-A total score at 12 weeks of therapy in Tenoten groups with both dosing schemes is expected to reduced by at least 10 units, in Placebo - by no more than 6 units (difference – at least 4 points). Population variance for total score change was $\sigma^2=44$ (based on preliminary analysis).

HAM-A mean score changes after 12 weeks in Tenoten groups for both dosing schemes are expected to differ by less than **3** points. Population variance was accepted as 6^2 =44 (based on preliminary analysis).

According to the statistical criteria and the assumptions above, for evaluation of differences in various dosing schemes, group size will be **103** subjects for Tenoten group (each dosing scheme) and **52** subjects for Placebo group (each dosing scheme). To evaluate superiority of the study product over placebo at different dosing schemes the group size will be 58 subjects for Tenoten group (each dosing scheme) and 26 subjects for Placebo group (each dosing scheme). The final sample size will be **103** subjects for Tenoten groups (each dosing scheme) and **52** subjects for Placebo group (each dosing scheme).

Given potential withdrawal of at least 20% subjects during the study for various reasons, at least **390** subjects will be required to sign informed consent.

Statistical criteria

All statistical calculations will be made using two groups of statistical criteria:

- parametric to evaluate continuous and interval random values;
- nonparametric to obtain:
 - evaluations of equality/inequality of proportions of the subjects upon their comparison for various visits,

- analysis of frequencies of the features compared, and
- evaluation of continuous and interval random values in case of non-compliance with normal random distribution.

Parametric criteria

Prior to analysis using parametric statistics, data samples under comparison will be tested for normality (the Kolmogorov-Smirnov test). Data normalizing transformations (e.g. Box-Cox, Yeo-Johnson etc.) would be applied if necessary.

The following parameters and approaches are to be used:

- 1. To evaluate the differences in continuous variables obtained in one group at two different visits Student's test for matched samples.
- 2. To evaluate time changes in parameters compared analysis of variance (ANOVA) or modified repeated measures covariance (ANCOVA).

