- 3. In case of multiple comparisons of the groups various corrections for multiplicity will be used, e.g. Dunnett, Tukey, Scheffe, Holm adapted test, etc.
- 4. Generalized Linear Models and/or Mixed Linear Models will be used in case of abnormal data distribution.
- 5. Selection of the type of distribution, specification of factor and covariance structures of the model will be made using fit-statistics such as AIC (Akaike information criterion).

The following SAS software programs are supposed to be applied to the above listed tests and techniques:

- UNIVARIATE: normality verification of the distributions under comparison;
- CORR, MEANS calculation of descriptive statistics
- TTEST Student's test with all modifications;
- GLM generalized linear models for analysis of time changes (ANOVA, ANCOVA);
- GENMOD generalized linear models.
- MIXED mixed linear models.

Non-parametric criteria

Below are potential types of comparisons with relevant criteria:

- 1. To evaluate time changes in the parameters compared Friedman test, nonparametric analogue of repeated measures analysis of variance.
- For frequency analysis of contingency tables 2×2 χ2 (if the frequency under comparison > 5) or exact Fisher's test (if one of the frequencies under comparison < 5).
- Cochran-Mantel-Haenszel test (modified χ2 test for multiple comparisons) to perform frequency analysis based on independent strata.

4. For frequency analysis of data on presence/absence of an event or outcome during repeated measurements (contingency tables with dependent strata) – survival analysis.

To perform the above-mentioned nonparametric statistical analysis the following SAS procedures are to be used:

- FREQ Friedman test, χ^2 test and/or exact Fisher's test; Cochran-Mantel-Haenszel test.
- LIFETEST survival analysis.
- NPAR1WAY Mann-Whitney test.

Safety parameters

Adverse events recorded during the study will be grouped into frequency tables by severity, seriousness and relationship with the study drug.

Data presentation

Descriptive statistics will be provided for each study continuous / interval variable. Numerical data will be presented by mean, standard deviation, min and max values. Comparisons suggesting statistical conclusion will have the relevant confidence intervals. Outliers will be analyzed individually. The data will be grouped by visits. The categorical variables will be presented as frequency tables by visits.

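### No single primary model in HAM-A points is fixed: the selection rules can move the Week-12 comparison off the scale of the hypotheses and margin, and baseline HAM-A is not a named covariate

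*Combined protocol and SAP*

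**What the plan says.** Evaluation of sample size, items 1.8.1 and 1.8.2, compares mean HAM-A reduction (initial minus final score) between each dose and placebo. Item 1.8.3 gives "null and alternative hypotheses on equivalence of the study product with dosing scheme 2 tablets 2 times a day" and the other scheme, again on mean reduction, with "equivalence margin accepted as 0.15*M where M" is the mean baseline score. All three hypotheses and the margin are therefore in HAM-A points. Item 1.6 pools the placebo groups, and item 1.7 sets alpha at 0.05/3.

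Statistical criteria then gives general rules, with no exception for the primary endpoint:

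- Under Parametric criteria: "Prior to analysis using parametric statistics, data samples under comparison will be tested for normality (the Kolmogorov-Smirnov test". Neither the form nor the level of the test is given.
- Next: "Data normalizing transformations (e.g. Box-Cox, Yeo-Johnson etc.) would be applied if necessary".
- Nonparametric methods are listed for "evaluation of continuous and interval random values in case of non-compliance with normal random distribution".
- Parametric criteria, item 4: "Generalized Linear Models and/or Mixed Linear Models will be used in case of abnormal data distribution".
- Item 5: "Selection of the type of distribution, specification of factor and covariance structures of the model will be made using fit-statistics such as AIC".
- Item 2 offers, for changes over time, "analysis of variance (ANOVA) or modified repeated measures covariance (ANCOVA", and names no covariate.

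The SAS procedures listed (TTEST, GLM, GENMOD, MIXED, NPAR1WAY) are not tied to endpoints. Data presentation promises confidence intervals without naming their model or scale.

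**The concern.** The hypotheses fix a scale and the analysis rules do not. Two analysts following the same text could reach different primary analyses of the same data, some in HAM-A points and some not.

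The equivalence claim is the most exposed. It needs an interval for a mean difference in points to set against a margin in points. If the chosen analysis is on another scale, item 1.8.3 is not tested as written, and the superiority tests no longer concern the stated means. Which of these happens is settled only after the data are seen.

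A smaller matter is precision. Baseline HAM-A is collected at Visit 1, but no rule says that the primary comparison uses it.

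**Working it through.** **Inputs from Evaluation of sample size.** Variance of change 44; differences of 4 points (superiority) and 3 points (between doses); power 80%; alpha 0.05/3, two-sided for superiority and one-sided for equivalence; completers 103, 103 and 2 × 52 = 104 pooled placebo.

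**Assumed, because the documents do not say.** Form and level of the Kolmogorov-Smirnov test; group-by-group testing; whole-point scores; delta = 3 points (range 2 to 4), since M is not given; the baseline to Week-12 correlation rho; and k = final SD / baseline SD.

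**1. The plan's own figures.** Formula 1.9.1 gives 2(2.394 + 0.842)² × 44 / 4² = 57.6, so 58, as stated. The same formula with 3 points gives 102.4, so 103. The sizing thus matches an unadjusted difference in points. (Printed formula 1.9.2, with delta − |epsilon| = 3 and one-sided 0.05/3, gives 113.7, so 114. That is a separate matter.)

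**2. Where each permitted route ends.**

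| Route | Scale |
|---|---|
| ANOVA or ANCOVA on raw change; mixed linear or identity-link model | points |
| Box-Cox or Yeo-Johnson, then a parametric test | transformed |
| Generalized model with another link | link scale |
| Mann-Whitney or Friedman as listed | ranks |

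Nothing in the text selects the first row.

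**3. How often the pre-test fires.** Simulated normal changes rounded to whole points, variance 44, 103/103/104, 20,000 runs:

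| Test | One group | Either dose group | Any of three |
|---|---|---|---|
| Lilliefors-corrected, 5% | 22% | 38% | 51% |
| Lilliefors-corrected, 1% | 6% | 12% | 17% |
| Uncorrected, 5% | 0.2% | 0.3% | 0.5% |

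Unrounded normal data fail the corrected 5% test in 4.7% of single groups, so the excess comes from whole-point scoring.

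**4. The margin after transformation.** With skew 0.5 and 310 subjects, the estimated Yeo-Johnson lambda ran from 0.79 to 0.96 (95% of 600 runs). With T(y) = ((y + 1)^lambda − 1)/lambda, T(13) − T(10) and T(10) − T(7) are 1.76 and 1.86 at lambda 0.788, and 2.73 and 2.76 at 0.963. Three points around a reduction of 10 are therefore about 1.8 to 2.8 transformed units (2 points: 1.2 to 1.8; 4 points: 2.3 to 3.7). The conversion depends on lambda and on location, and the plan gives no transformed-scale margin.

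**5. The margin with ranks.** Mann-Whitney on scores shifted by ±delta does test a points margin. With the true difference at the margin (103 vs 103, delta 3 or 4, skew 0, 0.5 or 1, pure shift), rank equivalence was declared in 1.3 to 1.7% of runs and t-based equivalence in 1.4 to 1.9%; nominal is 1.67%. The shift equals a mean difference only if the groups share a shape, and the plan does not state this procedure.

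**6. Baseline adjustment.** The variance ratio of ANCOVA to unadjusted change is k²(1 − rho²)/(1 + k² − 2 rho k).

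| k | rho 0 | rho 0.5 | rho 0.8 |
|---|---|---|---|
| 1 | 0.50 | 0.75 | 0.90 |
| 1.25 | 0.61 | 0.89 | 1.00 |

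The reduction is 50%, 25% and 10%, or 39%, 11% and 0%. It would be larger if the final SD were below baseline (k = 0.8: 61%, 43% and 36%). The rho = 0 column is the sizing convention of item 1.9.1.

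**7. Effect on power.** Superiority power for 4 points (103 vs 104) is 97.4% unadjusted, so it is not at risk. For equivalence at delta = 3 and no true difference, the standard error is sqrt(2 × 44/103) = 0.924 and power is 2Φ(3/0.924 − 2.128) − 1 = 73.6%. With baseline adjustment at k = 1 it is 89.5% (rho 0.5) or 80.4% (rho 0.8); at k = 1.25 and rho 0.8 it stays at 73.6%.

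**The case against.** Several points on the other side are fair.

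- **Type I error.** A reader might infer that letting the data choose the test inflates it. That is not shown. A gated procedure (Mann-Whitney if the corrected 5% test rejects in either group, otherwise ANCOVA) had type I error of 0.015 to 0.018 at nominal 0.0167. Free choice of the best of four analyses rejected in about 3.5% of null runs, where each alone gave 2.0 to 2.2%, but the plan does not license that choice. The transformation and generalized-model routes of the gate were not simulated.
- **Ranks.** A reader might infer that a rank analysis cannot test a points margin. It can, by the shift (Hodges-Lehmann) procedure in step 5. What stands is that the plan does not state it and that it needs a common shape.
- **Contradiction.** The two options for non-normal data are unranked alternatives rather than contradictory rules. Test, transform, then nonparametric can be read as a sequence, and item 5 can be read as applying only to the models of item 4. Neither reading names the primary model or ties it to points.
- **M is not numeric.** The points margin is itself not a number until M is known. True, but M then gives a margin in points, which a transformed analysis still cannot use directly.
- **Choice of remedy.** A raw-points repeated-measures model would answer the hypotheses as well as an ANCOVA. Accepted.
- **Protocol summary.** The document calls itself a protocol summary, so a fuller text may name the model. The point concerns the public text.

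**Conclusion.** The point holds as a gap between scale and model. The hypotheses and margin are in raw points, and the selection rules permit a primary analysis that is not. On a transformed or non-identity-link scale the margin cannot be applied directly; on ranks it needs an unstated procedure and an added assumption.

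The size is conditional. At the 5% level the pre-test could fire in 0.2% or 22% of single groups for the same rounded normal data, depending on a detail that the plan omits, so no firm frequency can be claimed. The variance reduction of 0 to 50% assumes a final SD of 1 or 1.25 times the baseline SD and rho from 0 to 0.8. It is nil if the sponsor's ANCOVA would already include baseline.

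A reader might also infer that the plan rules out an analysis in points, or that a wrong conclusion is likely. The documents support neither: points-scale routes are permitted, and no reversed conclusion has been shown. The change should be made because it settles the primary analysis before the data are seen, at almost no cost.

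**What to change.** For the primary endpoint, replace the selection rules with one pre-specified model of untransformed HAM-A change at Week 12. Use arm (two doses, pooled placebo) as factor and baseline HAM-A as covariate. This can be an ANCOVA or the Week-12 contrast of a baseline-adjusted repeated-measures model with a pre-specified covariance structure. With baseline as covariate, the treatment contrast is the same for the Week-12 score and for change, apart from sign.

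Take all three tests from that model:

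- Superiority: two contrasts at two-sided 0.05/3, with 98.3% intervals (1 − 0.05/3).
- Equivalence: the 96.7% two-sided interval (1 − 2 × 0.05/3) must lie wholly within ±delta points.

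State that 0.05/3 governs these three tests, rather than the open list of corrections in Parametric criteria, item 3. For this endpoint drop the normality pre-test, the transformation step and AIC choice of distribution or factors. Keep transformed and rank analyses as sensitivity analyses only.

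The cost is one degree of freedom and SAP wording. Baseline HAM-A is already collected, and ANCOVA, PROC GLM and PROC MIXED are already listed. No extra patients are needed: with equal baseline and final SDs, superiority power is 98.0% at rho 0.9 and higher at lower rho. Handling of missing values and the numerical value of M are separate matters that this change does not settle.

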Procedure/visit	Visit 1 (Day 1)	Visit 2 (Week 4±3 days)	Visit 3 (Week 8±3 days)	Visit 4 (Week 12±3 days)
Informed consent	+			
Collection of complaints	+	+	+	+
Medical history	+			
Physical examination	+	+	+	+
HADS scale filling	+			
HAM-A scale filling	+	+	+	+
EQ-5D-3L questionnaire filling	+			+
Pregnancy test	+			
Concomitant therapy	+	+	+	+
Inclusion/exclusion criteria	+			
Randomization and prescription of study therapy	+			
Study drug supply	+	+	+	
Study drug accountability, compliance assessment		+	+	+
CGI scale filling				+
Evaluation of treatment safety		+	+	+

Schedule of study procedures

Statistical Analyses

Samples

Total set includes all the subjects who have signed ICF. This sample will consider all adverse events throughout the study, including those occurred prior to the study therapy.

The sample including all subjects who received at least one dose of the study product to be used for *analysis of the study treatment safety and tolerability* (*Safety population*), as all adverse events identified after the study product administration will be recorded.

Full Analysis Set This sample will consist of all enrolled subjects, except for those who met at least one of the following criteria:

- 1) failure to meet inclusion/non-inclusion criteria;
- 2) subject failing to take any dose of the study drug;
- 3) absence of any data on the subject after the study drug administration.

This was the best set for the Intention-to-treat method, so it will be used in the *Intention-to-treat efficacy analysis of the test therapy*.

Per Protocol set. This sample includes all subjects who completed the therapy as per the study protocol, without any missing visits or major protocol deviations. This set will be used in the *Per*

Protocol efficacy analysis of the test therapy.

Mean value of the total set for the relevant day will be used to fill lacking/missing data.

Data treatment and all statistical calculations under the protocol will be made using SAS-9.4 statistical software.¹⁰

Evaluation of sample size

The sample size was assessed in accordance with the following rules and assumptions:

- 1. Statistical assumptions
 - 1.1 the power of statistical tests 'P = (1β) ' is 80% (the probability of correct rejection of the null hypothesis is 0.8)
 - 1.2 the probability of type 1 error 'a' is less that 5% (the probability of false acceptance of the alternative hypothesis is less than 0.05);

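### The correction governing the three primary hypotheses is not named; if it is flat 0.05/3, equivalence power at 103 per dose is about 74%, not 80%, and naming Holm would restore it if Tenoten beats placebo as planned

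*Combined protocol and SAP*

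**What the plan says.** Under Evaluation of sample size, item 1.2 limits type I error: "the probability of false acceptance of the alternative hypothesis is less than 0.05". Item 1.7 says that α is to be "corrected by introducing the relevant correction for three hypotheses", with the value 0.05/3. Item 1.8 lists the three: each Tenoten dose against pooled placebo (1.8.1 and 1.8.2), and equivalence of the two doses within a margin δ = 0.15×M, where M is the mean baseline score (1.8.3). Item 1.3 fixes sidedness: "statistical criteria of intergroup comparisons will be two-sided, equivalence criterion one-sided". Item 1.1 sets 80% power.

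Under Statistical criteria, Parametric criteria, item 3 covers multiple group comparisons and says "various corrections for multiplicity will be used, e.g. Dunnett, Tukey, Scheffe, Holm adapted test", ending with an et cetera. It does not mention the three hypotheses, and no other text says which procedure decides them. Data presentation asks for confidence intervals with every comparison that leads to a statistical conclusion.

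The stated sizes are 58 per Tenoten dose for superiority and 103 for the comparison of doses. The final plan is 103 per Tenoten dose and 52 per placebo scheme.

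**The concern.** The only numeric rule for the primary hypotheses sits in the sample-size section, and the analysis section offers a menu. A reader cannot tell whether 0.05/3 binds the analysis or served only for planning. The listed methods are not interchangeable here. Dunnett, Tukey and Scheffe are built for families of mean differences, whereas this family mixes two two-sided superiority tests with one equivalence test. Holm works on p-values of any kind, and it rejects everything that flat Bonferroni rejects.

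Equivalence is the hypothesis that sets the size of the trial. If it is tested at 0.05/3, the trial has less power for it than the plan states.

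**Working it through.** **Inputs from the plan.** Variance of change 44; superiority effect "difference – at least 4 points"; 103 per Tenoten dose; pooled placebo 52 + 52 = 104; α = 0.05/3 = 0.01667; power 0.80, so β = 0.20.

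**Assumptions.** Margin δ = 3 and true dose difference ε = 0. The plan says only that the doses are expected to differ by less than 3 points. It does not give M; δ = 3 means M = 3/0.15 = 20.

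**1. The plan's own sizes.**
- Superiority, formula 1.9.1 at two-sided 0.05/3: 2(2.394 + 0.842)² × 44/4² = 57.6, so 58. This matches.
- Equivalence, formula 1.9.2, n = 2(z_α + z_{β/2})² × 44/3², with z_{β/2} = 1.282:

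| One-sided α | z_α | n |
|---|---|---|
| 0.05/3 | 2.128 | 113.7, so 114 |
| 0.025 | 1.960 | 102.7, so 103 |
| 0.05 | 1.645 | 83.7, so 84 |

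- The stated 103 also comes from formula 1.9.1 at two-sided 0.05/3 with 3 points in place of 4: 2(2.394 + 0.842)² × 44/9 = 102.4, so 103.

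**2. Equivalence power at 103 per dose.** SE = √(88/103) = 0.924 and 3/SE = 3.246. Power of two one-sided tests (TOST) = 2Φ(3.246 − z_α) − 1:
- one-sided 0.05/3: 73.6%
- one-sided 0.025: 80.1%
- one-sided 0.05: 89.1%

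**3. Flat 0.05/3 against Holm.** Holm compares the ordered p-values with 0.05/3, 0.05/2 and 0.05. Equivalence gets the full 0.05 only after both superiority nulls are rejected. Simulation: 1,000,000 replicates, groups of 103, 103 and 104, normal arm means with variance 44/n, a true benefit of 4 points in both doses.

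| | Flat 0.05/3 | Holm |
|---|---|---|
| Superiority, each dose | 97.4% | 98.6% |
| Equivalence | 73.7% | 88.6% |
| All three | 71.7% | 87.8% |

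With the equivalence step capped at one-sided 0.025, equivalence power is about 80%.

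**4. Sensitivity of equivalence power.**
- True benefit over placebo (Holm, uncapped): 85.5% at 3 points, 79.6% at 2, 75.1% at 1, 73.9% at 0. Flat 0.05/3 stays near 73.6% throughout.
- Margin: at M = 18 (δ = 2.7), 57.2% flat and at most 79.8% with Holm; at M = 22 (δ = 3.3), 85.1% and at most 94.6%.
- True dose difference: at 0.5 point, 66.9% and at most 83.9%; at 1 point, 50.0% and at most 69.4%.

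**5. Error.** In the unfavourable case both doses beat placebo and truly differ by the margin. With true effects of 4 and 7 points, false equivalence is declared in 1.7% of trials under flat 0.05/3, 5.0% under Holm and 2.5% under Holm with the cap. All are within the familywise 5%.

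**The case against.** The strongest reply is that there is no contradiction. Item 1.7 ties a number to the three hypotheses, and item 3 is a general line that may concern only other comparisons, such as the secondary endpoints at several visits. A reader might infer that the sponsor means to choose a correction after seeing the data, or to stack Dunnett on top of 0.05/3. The documents do not say either, and this point does not rest on it. What remains is that item 1.7 stands under sample size and nothing carries it into the analysis.

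Second, flat 0.05/3 is a valid, conservative rule and gives matching simultaneous intervals, which suits the confidence-interval requirement in Data presentation. That is a fair reason to keep it, but it does not repair the power: under that rule and the assumptions above, 103 falls short of 80%.

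Third, a reader might conclude that 103 was computed at one-sided 0.025. That is not proven, because formula 1.9.1 at 0.05/3 gives 103 as well. The cap at 0.025 is therefore an option, not a recovery of the plan's intent.

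Fourth, 89% could be read as a general result. It is not: it needs both superiority tests to succeed, a 3-point margin, no true dose difference and a last step at one-sided 0.05. That last step is also why false equivalence can rise threefold.

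**Conclusion.** The point holds in a limited form. The plan does not say which correction governs its three primary hypotheses in the analysis. If flat 0.05/3 does, equivalence power at 103 per dose is about 74% against the stated 80%, and formula 1.9.2 needs 114. This rests on variance 44, a 3-point margin and a true dose difference of zero; M is not given, and the result moves materially with it.

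Under the same assumptions and the planned 4-point benefit, Holm gives about 89% uncapped or about 80% capped, with no more patients and familywise error still at or below 5%. The gain shrinks to almost nothing if Tenoten does not beat placebo, but Holm is never less powerful than the flat rule. The change should be made. It does not mean that the planned flat rule is invalid.

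**What to change.** State, both in item 1.7 and in the Parametric criteria, that the two two-sided superiority p-values and the TOST p-value are tested by Holm at familywise 0.05. Limit the open list in item 3 to other comparisons. Say whether the equivalence step is capped at one-sided 0.025, and give the value of M, or of the margin in points, on which the power rests.

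State the downsides beside the rule: the false-equivalence risk at the margin (up to 5.0% uncapped or 2.5% capped, against 1.7% under the flat rule), the dependence of the gain on superiority, and how the required confidence intervals will be built, since they follow Holm decisions less directly than Bonferroni ones.

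If the sponsor prefers flat 0.05/3, say that it governs the analysis and restate equivalence power as about 74% at 103 per dose. Either route is a change of wording with no change in sample size.
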